Sixty-six African American older adults (53 female; Mean age = 69.4 ± 4.9 years) were screened and scheduled for baseline testing in Pittsburgh. Of this group, 48 (~90%) successfully completed the baseline measurements and were subsequently randomized and enrolled. First, we successfully maintained heart rate in our prescribed heart rate zone. On average, participants in the Dance group maintained a heart rate (HR) of 68.3% of their APMHR throughout the intervention classes. Thus, our dance intervention was effective at maintaining a HR intensity

in the target range and can be considered a form of moderate-intensity PA. Second, enrollment and adherence continued to improve with each wave of the intervention so that attendance rates in the last wave were >70% for both groups. Attendance rates improved from the first to the second cohort, and enrollment rose from 7 participants in the Dance group and 3 in the Education group in wave 1, to 12 and 11 participants in these two groups, respectively, in wave 2. Importantly, we learned successful advertising methods and tactics to improve attendance. We plan to implement several strategies to further promote attendance in the present study (e.g., transportation support, raffles, performance summaries). We found that participants were overwhelmingly enthusiastic about both interventions. On average, participants rated the enjoyability of the Dance and Education interventions as 5.0 and 4.6, respectively, on a scale of 1-5. In fact, when asked what they would improve about the intervention, many participants suggested that we make the intervention duration longer.

1.3 STATISTICAL ANALYSIS:

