1.3.1 General Approach. We will analyze data in an intent-to-treat (ITT) manner such that all participants, regardless of whether they complete the intervention, will be invited to return for the follow-up sessions and will be included in primary analyses. Secondary analyses will be conducted using a per-protocol approach, which restricts the analysis to the participants that completed the intervention. All cognitive and neuroimaging data will be interrogated for normality, and symmetry, and any non-normal data may be transformed based on the distribution of error terms. Any data that cannot be transformed will be analyzed using non-parametric tests. Non-parametric regression models will be used for continuous variables when necessary. We will examine the data for potential outliers. If it is determined that outliers are due to misreporting of data or administrative error, we will delete them from the analysis. If the outliers are not due to misreporting of data or administrative error we will conduct the analysis with and without outliers included. Outlier de-weighting will be conducted on voxel-wise MRI data to remove the influence of anomalous voxels in the analysis. All analyses will be two-tailed. We will first summarize baseline demographic and brain characteristics of the sample and intervention groups using descriptive statistics and statistical hypothesis testing. Descriptive statistics will include mean, median, standard deviation, range for continuous variables, and frequency for categorical variables. Statistical tests will be conducted using t-test, ANOVA F-test, Chi-square test, correlations (Pearson or Spearman) as appropriate. Our primary goals are to examine whether the intervention improves cognitive and brain health. To test these hypotheses, we propose to use a General Linear Mixed Model (GLMM) in standard neuroimaging and statistical packages. Effects of Time (baseline, 6-month), Group (Dance, Education), and Time by Group interactions will be examined. Post-hoc comparisons using least square means will decompose any significant interactions and will be plotted to illustrate the direction of the effect. Mean differences between groups for all cognitive and neuroimaging outcome measures will be derived using linear contrasts and multiple comparisons will be corrected by standard protocols. Differences in baseline characteristics will be accounted for by using covariance

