Aim 3 proposes to explore physiological and socioemotional mechanisms of the dance intervention. We plan to explore our hypotheses using several different approaches including simple mediational models applying the change score method and will estimate whether the dance intervention (predictor) on *changes* in cognitive function outcomes are mediated through *changes* in the suspected mediators. Goodness-of-fit will be assessed through standard summary indices (e.g., RMSEA, CFI) and model assessment via residual analyses will be performed. Total, indirect and direct effects will be estimated. Additionally, we will explore mediation applying the half-longitudinal approach proposed by Cole and Maxwell as well as an autoregressive mediational approach. Finally, we will explore recent advancements in repeated measures mediation analyses developed by Preacher and Hayes. Depending on the results from simple mediational modeling, we may also combine mediators into a multiple mediator model to develop a more comprehensive picture of these pathways.

1.3.2 Power Analyses. Our planned sample size of 180, with randomization of 90 participants in each group, is based on effect sizes from preliminary data. Even when accounting for attrition and retention of ~70% of participants (65 in each group), we are sufficiently powered to detect effects in cognitive and brain outcomes and to test for mediation.

1.3.3 Cognitive performance. Our prior PA interventions have found moderate sized effects on cognitive function after 6-months with a Cohen’s d ranging from 0.40 to 0.80 depending on the outcome (23). In our analysis of the pilot data from the African Dance intervention with only 19 participants (9 in the Dance group) we estimate similar or greater effect sizes of ~.70. If we estimate an effect of 0.70, 65 participants per group after attrition will provide us with >91% power to examine our primary hypotheses.

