1.3.4 Brain Volumetrics. Our prior 6-12 month PA interventions have used between 30 and 60 subjects per group with Cohen's d ranging between 0.40 and 0.50 using similar analysis approaches (18, 20, 27, 41, 42). Cross-sectional research has reported significant effects of PA on brain volume with as few as 32 subjects and effect sizes between 0.50 – 0.60 (24, 40, 42–44). Preliminary data on 37 African Americans from one of our prior studies suggest that cross-sectional differences between African Americans engaging in PA compared to those not engaging in PA are larger than for whites (Cohen's d = 1.83). These studies argue for a moderate-to-large effect of PA on brain volume depending on the sample, the measure of PA and fitness, and the brain metric used. If we estimate a conservative effect size of 0.50, 65 participants per group will be sufficient to detect differences in brain volume at 81% power.

1.3.5 Diffusion tensor imaging. Changes in white matter have been detected in PA interventions in as little as 6-months with only 50 subjects (45). In a 12-month PA intervention, we found increased FA with only 35 subjects in each group with an estimated effect size of 0.70 (41). Based on an estimated effect size of 0.75, we should have >85% power with 65 participants per group to test our main hypotheses as well as enough power for exploratory analyses.

1.3.6 Task-evoked activity. Task-evoked brain imaging studies of PA have found statistically significant effects with 30 - 50 subjects per group with effect sizes ranging between 1.0 and 1.3 depending on the region examined and the task employed (26). Cross-sectional studies of fitness on brain activity report even larger effects up to 1.70 (36, 46, 47). These patterns indicate a large effect size of PA on brain function, so 65 participants per group will provide us with substantial power to test our main aims and hypotheses.

1.3.7 Connectivity. With only 65 people, we have shown that a PA intervention is effective at enhancing functional connectivity in prefrontal-inhibitory networks (27). The difference between the groups for prefrontal cortex connectivity was .15 with a standard deviation of .10 suggesting an effect size of 1.5 (Cohen's d). Therefore, similar to the effect sizes and power for the other measures, 65 participants per group should be sufficient for detecting changes as a function of the intervention with >85% power.

1.7 PROCEDURES:

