After the completion of the measures and sessions described above the participants will be randomly assigned to one of two groups: (a) The Dance condition will consist of approximately 180 minutes per week of moderate intensity African Dance, or (b) an Africana Culture control condition that will consist of 180 minutes per week of mixed-programming related to African Culture, including art projects, cooking, and films. We will use a computer randomization protocol that will incorporate a verification that all session visits have been completed and data entered into the database. We will use a stratified permuted block randomization algorithm with equal allocation to one of the two groups. The use of this strategy will ensure treatment balance on the two factors of age at study entry ($=<70, >70$) and gender. Once randomized, an assigned staff member will contact the subject via phone with the group information. On this contact, the staff

member will give information such as date, day, time, and location of the subject's first intervention session.

1.10 EXERCISE INTERVENTION GROUPS:

1.10.1 African Dance Group. Participants in the Dance condition will begin by dancing at reduced intensity during the first week of the program and will gradually increase their dancing intensity each subsequent week until they reach 40-60% of their heart rate reserve for all of the dance class. All dance sessions start and end with 5-10 minutes of active stretching for the purpose of warming up and cooling down. As the participants will be low active at baseline, the prescribed intensity will be 50–65% of the maximum heart rate reserve for weeks one to four and 65–80% for the remainder of the program. Participants will be fitted with a Polar Bluetooth Smart heart rate sensor around their chest and be encouraged to dance within their target heart rate zone by fitness staff. Continuous heart rate readings of all participants will be displayed in real-time via the Polar Team app on an iPad or other tablet. Certified exercise instructors will closely monitor attendance, intensity, frequency, and safety. Dance sessions will occur three days/week at one of two study sites for the duration of the intervention.

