1.10.2 Africana Culture Group. The control group will focus on learning about and experiencing Africana culture through interactive class discussions, lectures, and hand-on demonstrations. This goal for this group is 150 minutes of contact per week so the social component of the Dance intervention is matched. However, crucially, the control group will not participate in any aerobic activities; the majority of their activities will be conducted in a sitting position. Adherence is also tracked in this group, and study participants are encouraged to attend as many classes as possible of the offered sessions (3 classes per week). Each class is expected to last 60 minutes with 5-10 minutes for taking attendance and making administrative announcements at the beginning/end of the class.

Session Compliance. Participants in the study will be completing the African Dance classes or Culture classes under supervised conditions. We will monitor compliance during the classes by having trainers or staff monitor attendance, duration of the dance, ratings of perceived exertion, and heart rate intensity throughout the class period.

Based on the above, we have operationally defined compliance to the intervention as those participants meeting the prescription of either 150 minutes per week of moderate intensity Dance (Group 1), or 150 minutes per week of Africana Culture class (Group 2). Compliance to these prescriptions will be based on the information gathered from the supervised sessions.

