Given the continued challenges of navigating the COVID-19 pandemic, we requested to modify our recruitment/randomization accrual and targeted sample size for the study titled "Rhythm Experience and Africana Culture Trial (REACT II)" on August 29th, 2023. We have determined that we will have sufficient statistical power to test our primary aims with a reduction in the targeted sample size from 180 to 150.

The recommended changes were approved by the meeting of the Data Safety and Monitoring Board on August 29, 2023.

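### The 81% brain-volume power is for 65 analysed per arm and was not restated when the target fell to 150 (about 71–73% on the same calculation); secondarily, no sensitivity analysis covers correlation among classmates.

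*Combined protocol and SAP*

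**What the plan says.** **Power.** Protocol 1.3.2 and the SAP power text start from 180 randomised, 90 per arm, with roughly 70% retained, given as 65 per arm. For brain volume at d = 0.50, protocol 1.3.4 and the SAP state that "65 participants per group will be sufficient to detect differences in brain volume at 81% power". For cognition at d = 0.70, protocol 1.3.3 and the SAP state that "65 participants per group after attrition will provide us with >91% power". Protocol 1.11 names executive functioning and hippocampal volume as the primary outcomes, so both figures bear on a primary outcome.

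**Sample size change.** The SAP's closing paragraphs, dated August 29, 2023, report "sufficient statistical power to test our primary aims with a reduction in the targeted sample size from 180 to 150". They give no effect size, retention rate or power figure. The protocol carries the same date, and its summary and section 1.3.2 still use 180.

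**Delivery and model.** Randomisation is individual, stratified by age and gender (1.9). Both arms then attend classes three times a week for 6 months: "Participants in the study will be completing the African Dance classes or Culture classes under supervised conditions" (1.10.2, Session Compliance). For Dance, "Dance sessions will occur three days/week at one of two study sites for the duration of the intervention" (1.10.1). The model in protocol 1.3.1 and the SAP is: "Effects of Time (baseline, 6-month), Group (Dance, Education), and Time by Group interactions will be examined". The sensitivity analyses named in 1.3.1 concern missing data and outliers. The hierarchical regressions in 1.3.1 and 1.11 concern fitness change and imaging predictors, not classes.

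**The concern.** A power figure belongs to a particular number analysed. The trial now aims for 150, but the only quantified power for brain volume assumes a number per arm that 150 would yield only with much better retention than planned. A null hippocampal result would be read against an 81% that no longer describes the design.

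The second issue is separate and conditional. People who share an instructor, a room and a social group for 6 months may change in similar ways. If they do, a model that treats them as independent understates the standard error of Time by Group, and its false-positive rate exceeds the nominal level. With no class term and no sensitivity analysis, a reader of the results could not tell whether this had happened.

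**Working it through.** **Inputs.** From the documents: d = 0.50 (1.3.4) and 0.70 (1.3.3); 65 analysed of 90 per arm, or about 70% (1.3.2); two-sided tests (1.3.1); equal allocation (1.9); target of 150, so 75 per arm (SAP closing paragraphs). Assumed: alpha 0.05, which the documents do not state.

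**Formula.** Two-sample t-test, df = 2n − 2, noncentrality d × √(n/2), with n per arm.

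**Reproducing the plan's figures (65 per arm).**
- Brain volume: 0.50 × √32.5 = 2.85, giving 80.8%, which matches 81%.
- Cognition: 0.70 × √32.5 = 3.99, giving 97.7%. The stated figure is therefore a loose lower bound.

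**Numbers analysed at 150.** 75 × 65/90 = 54.2, so 54 per arm. 75 × 0.70 = 52.5, so 52–53 per arm. Keeping 65 per arm would need 65/75 = 86.7% retention.

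| Analysed per arm | Power, d = 0.50 | Power, d = 0.70 |
|---|---|---|
| 65 | 80.8% | 97.7% |
| 54 | 73.1% | 95.0% |
| 53 | 72.2% | 94.6% |
| 52 | 71.4% | 94.2% |

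No clustering enters this table. The fall from 81% to 71–73% comes from the smaller target alone.

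**Clustering (illustrative).** Assumed: 54 per arm, fixed class membership, ICC of 0.01, 0.02 or 0.05 for the 6-month change, and classes about the size of the pilot's second wave, where enrolment per group rose "to 12 and 11 participants in these two groups, respectively, in wave 2" (1.2.3). 75/12 = 6.25 and 75/11 = 6.8, so k = 6–7 classes per arm and m = 54/k = 9.0 to 7.7 analysed per class. The design effect is DE = 1 + (m − 1) × ICC, and the noncentrality becomes d × √(n/(2 × DE)). Type I error is from a simulated t-test that ignores class (200,000 replicates); at ICC 0 it returned 4.9–5.1%.

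| ICC | DE | Type I error, both arms clustered | Type I error, Dance only | Power, d = 0.50 | Power, d = 0.70 |
|---|---|---|---|---|---|
| 0.01 | 1.07–1.08 | 5.8–5.9% | 5.5% | 70% | 93–94% |
| 0.02 | 1.13–1.16 | 6.5–7.0% | 5.8–5.9% | 67–68% | 92% |
| 0.05 | 1.34–1.40 | 9.1–9.8% | 7.0–7.3% | 59–61% | 86–88% |

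The power columns take both arms as clustered. Over 4–10 classes per arm, type I error at ICC 0.05 ranges from 7.5% to 12.5% with both arms clustered and from 6.3% to 8.8% with Dance only. For cognition, power at d = 0.70 stays at or above 91% up to DE = 1.19 at 54 per arm, that is, an ICC of 0.192/(m − 1) = 0.024–0.029.

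**The case against.** **The planned analysis is not a two-sample t-test.** It is a repeated-measures mixed model with covariate adjustment, fitted to all available data, and the documents do not say which SD the 0.50 refers to. If it is the raw-score SD, baseline information raises power. At 54 per arm without clustering, power is about 81% at a baseline-to-follow-up correlation of 0.42 (baseline-adjusted) and 82% at 0.60 (change score). At 0.70, baseline-adjusted power is 95%, or 86% with a design effect of 1.40. This stands as a possibility. A reader might infer that the 81% leaves no room for any loss, or that the trial is underpowered at 150. The documents support neither; they show only that the calculation matching the 81% gives 71–73% at the new target. Equally, no correlation is stated, so the gain cannot be credited to the plan.

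**The clustering figures are assumed.** The pilot counts are enrolments per wave, not class sizes, and the pilot text does not reconcile: it reports 48 randomised and enrolled, while the waves sum to 7 + 3 + 12 + 11 = 33. Nothing fixes participants to one class. Individually monitored heart-rate zones (1.10.1), blinded assessors (1.7.6) and outcomes measured outside class may keep the ICC small. All of this stands, and it is why the point is secondary.

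**The remedy does not remove any inflation.** Correct: keeping the primary model means that the extra analysis can reveal a problem but not cure it. It still gives a reader something to check the primary result against, at little cost.

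**Conclusion.** The main point holds. The stated brain-volume power does not describe the current target. On the plan's own effect size and retention it is about 71–73%, assuming alpha 0.05, independent participants and no gain from baseline correlation. Cognition is not affected in the same way: 94–95% under independence keeps the stated bound, so the assertion of sufficient power is supported for executive functioning at the planned effect size.

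The clustering point holds only conditionally. The shared classes and the missing term or sensitivity analysis are facts of the documents; the size of any effect is not. At the assumed ICCs and 6–7 classes per arm, type I error would be about 6–10% with both arms clustered and about 5.5–7% with Dance only. A reader might infer that the primary test is invalid, or that clustering explains the fall from 81%. The documents support neither. This part is a cheap improvement, not an error in the primary analysis.

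**What to change.** **Power text.** In protocol 1.3.2–1.3.4 and the SAP power text, including its closing paragraphs, restate power at 150: about 73% for brain volume and 95% for cognition at 65/90 retention. State alpha, the SD to which d refers, any baseline-to-follow-up correlation relied on, and that participants are assumed independent. If another retention or correlation is intended, give it and the power that follows. The cost is wording, and a less favourable figure unless a baseline correlation is justified.

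**Clustering.** Keep the primary model. Record each participant's class (or, if people mix across classes, main class by attendance, or wave) and site. Prespecify one sensitivity analysis for the two primary outcomes: a class-by-time random effect, class nested within arm, with Kenward-Roger degrees of freedom. Report its estimate, interval and ICC beside the primary result.

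The cost is one recorded field and one extra model. Attendance is already monitored (1.10.2), and at randomisation staff give each subject "information such as date, day, time, and location" for the first session (1.9). Class can therefore probably be recovered, though no stored identifier is described.

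The limits should be stated in advance. With few classes the model is imprecise: using class-level degrees of freedom (2k − 2) and 4–10 classes per arm, its power at d = 0.50 is 59–69% even at ICC zero. Non-significance there should not by itself overturn the primary result, and a zero variance estimate should not be read as proof of no clustering. Nor can the model separate an instructor from an arm if one instructor teaches the whole arm.

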1.11 ANALYSIS PLAN

Our analysis plan has proposed an intent-to-treat analysis where all participants, regardless of whether they complete all sessions, will be invited to return for follow-up assessments. However, there will likely be some participants that refuse to return for follow-up assessments. “Lost to follow up” will be defined here as missing data that is contributing to the primary outcomes (executive functioning and hippocampal volume). The reason will be recorded (i.e., missed visit due to traveling, illness). These criteria and documentation will also be applied for any discontinued subjects with the reasons for discontinuation being recorded (i.e., moving out of state).

We propose to use all available data in the planned analysis for testing our primary outcomes. We will assess the missingness of data consistent with the assumptions of the modeling approach described above. That is, we will examine the randomness of missing data and examine if the data is missing completely at random (MCAR) or missing at random (MAR). Parameters of the GLMM will be estimated using the maximum likelihood estimation or restricted maximum likelihood methods that are known to produce consistent and efficient estimates under MAR.

Imaging data analysis. We will first analyze each imaging outcome (e.g., volume) separately from every other imaging outcome (e.g., fMRI). But, once voxel-wise associations related to the intervention are established, we could test, using hierarchical regression, the relative significance of each imaging measure to explain improvements in cognitive function with the intervention.

1.12 PARTICIPANT SAFETY:

The safety of study participants will be monitored throughout the study. Study participants will undergo an extensive screening prior to entering the trial to determine that it is safe for them to participate in the intervention. Safety is continuously monitored during the intervention during three supervised sessions per week. We are aware of the potential for serious adverse events (AEs) to occur with any type of exercise training. As such, the trial will take measures to reduce the risk of any adverse events or serious adverse events from occurring. All individuals involved in human subject's research where exercise training is involved, are trained and certified in CPR and First Aid. Included in the exercise stress testing room is an automated external defibrillator (AED), should it be deemed necessary. Lastly, protocols are currently in place to respond to any adverse events that include contacting emergency response personnel and facilitating their arrival to the correct rooms within the buildings at each intervention site.

The REACT II primary investigator has full responsibility for the safety of study participants. The Data Safety Monitoring Board (DSMB), is responsible for objectively monitoring study data for evidence of adverse effects attributed to the intervention. The DSMB also has the authority to recommend changes or pausing the trial until problems are resolved. All AEs experienced by the participant during the study (starting from consent signing until the end of study outcome collection) are to be documented and reported. Serious adverse events will be reported to the DSMB and the IRB. The REACT II trial will track the occurrence of:

- Serious Adverse Events (SAE)
- Unexpected events
- Unfavorable medical events that occur during intervention sessions

The trial has created two forms for adverse event reporting. These documents have been created based on the belief that trainers and staff should not be responsible for determining whether the event is related to the intervention or whether/how it should be reported to the IRB and DSMB. Only the PI will determine if the event is (a) expected or unexpected, and (b) related to the intervention. Based on responses to these questions, regardless of seriousness or relatedness, the trainer or dance instructor will complete a form documenting an adverse event. We have created a brief form for trainers and instructors (REACT II Adverse Event Form for Trainers) for this purpose. Trainers or staff would first document the event on this form. This form allows staff to circle the reported event (or provide an event not listed on the form). This completed document would be sent to the project coordinator who would then speak to the trainer and/or participant to find out more information about the event. The project coordinator would then complete the REACT II Event Evaluation Form based on this communication. This form has several sections with boxes available for documenting the chronicity (single occurrence, intermittent, persistent), whether the event was resolved or not, and whether it was related to the intervention and expected or unexpected. In particular, these forms are intended to clarify for the investigators, the IRB, and the DSMB, whether the adverse event was related to the intervention, and whether it was expected or unexpected. An example of an expected adverse event from the dance intervention would be muscle soreness which would be listed as a known risk in the IRB. An unexpected adverse event related to the intervention would be if someone falls during a class and injures an ankle. The PI will oversee the determination of these events and if there is any question about whether the event was related to the intervention, and its expectedness, the event will be discussed during weekly staff meetings. For DSMB purposes, all adverse events that are reported will be recorded and separated based on whether the event was related to the intervention, expectedness, severity, chronicity, and resolution.

1.13 DATA MANAGEMENT:

We appreciate the challenges associated with the organization, execution, management, and analysis of a clinical trial of this kind and recognize the importance of frequent communication between staff, students, analysts, and investigators. Protection of subject privacy and safety, meticulous QC, and prudent organization is the bedrock for success of a study like this, which will require a sizeable team of staff and students. For this study, [name] will maintain overall responsibility for DM and QC. [name] (biostatistician) will monitor database integrity for missing data, errors, outliers, and distributions.

IT staff will control permissions to the database to ensure proper access and DM by staff,

students, and investigators. We will store and link all behavioral and assay data on a HIPAA secure cloud-based server (REDCap) and may use other applications (e.g., the Flywheel application) for securely storing and accessing imaging data from the imaging center.

Data entry to the REDcap database will be completed within the BACH Lab that is directed by PI [name]. The data forms in REDcap are similar to the paper version of the forms that will be completed by participants and staff. All participant data will be stored and archived on a secure server. The server will be set for safe mode that allows two copies of each data to be saved. The data server will have a hard drive array, which is composed of a few hard drive disks. If one or two of the disks fail, the rest of the disks will back up the data of the failed disks automatically. By having the database on REDCap, all data is secure in case of a natural disaster or other calamity.

Missed Visits: All outcome collection must be reported and stored in the database. Therefore, if an outcome visit is missed or not collected, a missed visit form must be completed in REDCap. Once a missed visit form is completed, the data management team will indicate in the database that the outcome data for the specific measure is missed to follow up. All missing data in the database will require additional documentation regarding whether the data are “lost to follow up” or has been collected but there was a problem with transferring the data to the lab.

The missed visit form has three sections that must be completed:

- Time point of the missed visit
- Outcome that was missed
- Reason the outcome was missed

If a study participant misses multiple outcome measures during the same time point, one missed visit form can be completed if the reason missed is the same for each measure. Thus, staff do not have to complete a new form for each missed outcome for the same time point. For example, at follow-up, if the study participant missed the cognitive session and blood draw because the participant moved out of the area, this information could be completed on one missed visit form. If this study participant would also miss the baseline physical activity monitoring, a new form must be generated since this is a different time point.

1.14 QUALITY CONTROL:

This RCT demands rigorous QC to ensure consistency of the intervention procedures and protocols. Staff will be trained early in the first year to standardize protocols. We will also hold weekly meetings with all staff to ensure continuation of all protocols. Reports of QC will be a standard agenda item for Data Safety and Monitoring Board (DSMB) meetings. During the course of the study, we anticipate a turnaround of staff, graduate and undergraduate assistants, and these QC procedures will ensure compliance and uniformity of study protocol for the duration of the project.

1.14.1 Cognitive and MRI Quality Control. To maintain QC of the cognitive data, all possible administrators will receive QC training in Year 01 to administer the tests in a standardized way. These certification sessions will be conducted annually for maintenance of QC.

MR sequences will be established and piloted before the trial begins. The new joint Pitt-CMU Imaging Center is anticipated to be the location for the REACT II scans, which will have a research dedicated Siemens 3T machine. We will have monthly QC checks using phantoms and QC will be monitored for any changes over time. Before the start of the intervention, several staff members will be scanned to ensure equivalent contrast and image quality for each sequence. All imaging data will be uploaded to a server and will be examined by [name] laboratory to assess QC, proper sequences, and site- specific effects.

1.16 REFERENCES:

